11.4.4 Missing Data

Missing data due to dropouts have been accounted for in adjusted sample size. The missing data will be at random.

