6.4 Study Overview

To confirm or reject the hypotheses a prospective, double-blind, randomized controlled trial (RCT) is designed to investigate the clinical performance of resin-infiltration as early caries management in a caries-prone population.

This CIP describes a three-year longitudinal, prospective, randomized controlled trial in split mouth design. The study includes a clinical team involving one on-site Principal Investigator (Site-PI)/operator and one back-up Clinical Investigator (CI)/operator.

The clinical site will enroll 150 subjects (in the age range of 14 years or older) with 2 study lesions. If the lesion management provided in the study appears to be insufficient within the investigated period, the study will provide a maximum of 2 traditional restorations for free to participants. The patients will be evaluated at six time points over a period of 3 years. Lesion status and caries risk will be monitored at 6-month intervals, while radiographic evaluation will be conducted at 12-month intervals at 1-, 2- and 3-year recall visits.

7 Design of the Clinical Investigation

The study will be designed as a controlled, double blind, randomized, prospective trial with a three year follow-up period regarding to CONSORT²² recommendations as a single-center study to investigate the effect of caries infiltration as an alternative treatment option.

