11.2 Determination of Sample Size

Subjects recruited for this investigation will be selected from patients attending the clinical research area and recruited from advertisements (Attached). 150 patients aged 14 years and older will be recruited into the study to provide 150 resin infiltrated and control (no Treatment) lesions. Based on previous studies approximately 20% loss of these subjects will occur over the three year period producing a subject population of 120 who will be available for the 3 year recall.

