11.4 Statistical Analysis

11.4.1 Descriptive Statistics

For the digital subtraction procedure, the ANOVA for Repeated Measures, will be used to determine significance between the two groups ($p=.05$). The remaining endpoints will be listed as percentages rather than subjected to statistical analyses.

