A previous infiltration study by Martignon et al. [5] reported a 3-year difference of proportions of 37.8% (95%CI: 20.5-55.2%) with (resin infiltration (68%) vs. control (30%)). Based on this and with alfa = 0.05 and a power of 80% the calculated sample size (t-test; matched pairs) would be 23 lesion pairs (thus 23 participants) to find significant differences. However, this study aimed to enroll 150 participants to not only allow for a potentially high attrition rate (20%) over a period of 3 years, but also aiming to better quantify the efficiency of the treatment effect.

Statistical Analysis

All evaluations are performed by two trained and calibrated examiners. The primary outcome is proportion of lesions that required restorative treatment (filling) after 3 years as measured via dental examination. Differences between groups will be tested using Fisher's exact test and ANOVA for Repeated Measures for subgroup analysis based on caries risk. Secondary outcomes are change in categorical lesion depth (progression to next depth category lesion; E1->E2->D1->D2->filling) after 6 months and 1, 2 and 3 years as measured by pairwise comparison of radiographs as well as the influence of Icon treatment on clinical parameters. Differences will be analyzed with McNemar's test with 95% confidence interval (95% CI) and P = .05.

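### Drop-out is met only with a larger sample and an asserted mechanism, so the 3-year difference can be mis-sized if loss depends on earlier progression

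*Combined protocol and SAP*

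**What the plan says.** Section 11.4.4 deals with missing data in two sentences: "Missing data due to dropouts have been accounted for in adjusted sample size. The missing data will be at random". Section 11.2 expects "approximately 20% loss of these subjects will occur over the three year period producing a subject population of 120". The design is a "three-year longitudinal, prospective, randomized controlled trial in split mouth design", so a patient who leaves takes both lesions of the pair.

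The SAP (Statistical Analysis) makes the primary outcome the proportion of lesions filled by 3 years. It tests this with Fisher's exact test and names repeated-measures ANOVA for subgroups by caries risk. Categorical lesion depth is secondary: "Differences will be analyzed with McNemar's test". For subtraction radiography, protocol Section 11.4.1 says: "For the digital subtraction procedure, the ANOVA for Repeated Measures, will be used to determine significance between the two groups". Neither document names an analysis set, imputation, weighting, a likelihood-based model or a sensitivity analysis.

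Table 14.2 scores a lesion that reaches the middle or inner third of dentin, or a tooth with pulpitis, as a failure. Patients who are lost, withdraw, cannot be examined, or have a study lesion treated by an external dentist are scored as drop-out. Nothing says how they enter the analysis.

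**The concern.** Enrolling more patients answers the loss of information, not selective loss. Whether data are missing at random cannot be guaranteed in advance, yet it is stated as fact. McNemar's test needs both lesions at the visit tested, and Fisher's test needs an observed 3-year outcome. Classical repeated-measures ANOVA needs a complete set of whatever is repeated. Without imputation, the roughly 30 lost pairs (150 − 120) contribute nothing to the 3-year contrast, although many will have 12- or 24-month findings that predict it.

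If return for recall depends on what those films showed, the completers are a selected group. At stake is the size of the effect. The SAP needs few pairs for power ("with alfa = 0.05 and a power of 80% the calculated sample size (t-test; matched pairs) would be 23 lesion pairs") and enrols 150 partly to quantify the effect better. That larger sample shrinks the standard error and leaves any bias where it was.

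**Working it through.** **1. The plan's own figures.** 150 × (1 − 0.20) = 120, as stated. For the 23 pairs, using 32% and 70% progression and a 37.8-point difference, with two-sided alpha assumed: (1.960 + 0.842)² × (0.32 × 0.68 + 0.70 × 0.30) / 0.378² = 7.85 × 0.4276 / 0.1429 = 23.5, so 24, which is close. Allowing for 20% loss, 23 / 0.80 = 28.75, so 29 pairs. Power is not at issue; the remaining pairs serve estimation.

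**2. Inputs.** From Section 4.3.4 (the cited split-mouth study): progression at 1, 2 and 3 years of 16, 24 and 32% (infiltrated) and 53, 62 and 70% (control). The true 3-year difference is 38 points. *Assumptions:* the two lesions are independent; progression is permanent; about 20% of patients leave after month 12; leaving depends only on whether either lesion had progressed by then. Every such pattern is missing at random.

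**3. Split pairs by 12-month status.** New progression after month 12 is 0.32 − 0.16 = 0.16 (infiltrated) and 0.70 − 0.53 = 0.17 (control).
- Neither progressed: share 0.84 × 0.47 = 0.3948. Contribution to the difference: 0.84 × 0.17 − 0.47 × 0.16 = 0.1428 − 0.0752 = 0.0676, or 17.1 points within this group.
- At least one progressed: share 0.6052. Contribution: (0.53 + 0.16 × 0.17) − (0.16 + 0.53 × 0.16) = 0.5572 − 0.2448 = 0.3124, or 51.6 points within this group.
- Sum: 0.3124 + 0.0676 = 0.38.

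**4. Complete-pair difference.** With drop-out a (any progression) and b (none): [0.3124(1 − a) + 0.0676(1 − b)] / [0.6052(1 − a) + 0.3948(1 − b)].

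| a / b | Numerator / retained | Complete pairs | Random patient intercept only | Conditioning on 12-month status |
|---|---|---|---|---|
| 28% / 8% | 0.2871 / 0.7990 | 35.9 | 35.8 | 38.0 |
| 33% / 0% | 0.2769 / 0.8003 | 34.6 | 34.6 | 38.0 |
| 12% / 32% | 0.3209 / 0.8010 | 40.1 | 39.5 | 38.0 |
| 20% / 20% | 0.3040 / 0.8000 | 38.0 | 37.6 | 38.0 |

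The last column is 0.6052 × 51.6 + 0.3948 × 17.1 = 31.2 + 6.8 = 38.0. Within each 12-month group the completers are representative, and the group shares are known from everyone seen at 12 months. The fourth column is a logistic model with treatment, visit, their interaction and a patient intercept, fitted to all films and standardised at 3 years. It keeps most of the bias because a patient intercept does not represent the fact that a progressed lesion stays progressed.

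**5. Other assumed patterns**, with 20% loss after year 2, drop-out risk multiplied by 2 to 5, and within-pair correlation 0 to 0.5:
- driven by progression of either lesion: 35.7 to 36.8 points
- driven by the control lesion alone: 32.7 to 36.2
- driven by the infiltrated lesion alone: 40.3 to 46.3

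Loss that depends only on a baseline factor that does not alter the risk difference gives 38.0.

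**6. Scale.** At 120 independent pairs the standard error is √(0.4276 / 120) = 6.0 points; at 23 pairs it is √(0.4276 / 23) = 13.6. A 2.1-point bias is about a third of the former. If 38 points were observed in the 80% who complete, the extreme bounds are 0.8 × 38 − 20 = 10.4 and 0.8 × 38 + 20 = 50.4, both positive.

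**7. Primary outcome.** The documents give no filling rates, so no corresponding figure is computed for fillings.

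**The case against.** A reader might infer that the 3-year difference is biased under the plan's own assumption. The documents do not support that. Missing at random permits complete-pair bias but does not imply it, as the fourth row of the table and the baseline-only case show. The sentence in 11.4.4 may also be loose wording for completely at random, under which there is no bias.

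A reader might also infer that only complete cases are ever used. The documents do not say so, and Table 14.2 counts the worst lesions seen at the site as failures. The SAP also assesses lesion depth at earlier visits, so drop-outs' films do enter those comparisons. The gap concerns the 3-year contrast in patients scored as drop-out, and complete-pair use there is an inference from the tests named. Likewise, a fall in the analysed number below 120 would need missed-film rates that the documents do not give.

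The bias is small: about 2 points in the first scenario, with no reversal of direction. Losing both lesions together weakens differential loss, and the claimed blinding makes loss driven by one arm's lesion less natural than loss driven by either. All of this stands. What it does not supply is a method, an analysis set or a sensitivity analysis for a loss the plan itself expects.

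**Conclusion.** The point holds as a conditional one. The plan has no method for about 20% expected loss and states an uncheckable mechanism as fact. If drop-out depends on progression already seen, the 3-year difference can be too small or too large: 34.6 to 40.1 points against a true 38.0 when loss follows the 12-month status of either lesion, and 32.7 to 46.3 if it follows one arm's lesion alone. If drop-out is unrelated to outcome there is no bias. These figures rest on the cited radiographic progression rates and on assumed drop-out patterns; they are illustrations, not predictions. The sign of the effect is not in doubt. The change is worth making because effect size is a stated reason for enrolling 150. Separately, scoring a patient as drop-out because an external dentist treated a study lesion can tie missingness to the outcome itself, so Table 14.2 and Section 11.4.4 need to be reconciled.

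**What to change.** Replace Section 11.4.4, and mirror it in the SAP, along these lines:

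- All 150 randomised pairs enter the 3-year estimates of fillings (primary) and radiographic progression (secondary).
- Missing 3-year outcomes are handled by a method that conditions on each lesion's last observed status and keeps the pairing. One option is multiple imputation from the 6-month examination and the 12- and 24-month examinations and films of both lesions. Another is a discrete-time progression model with patient-clustered standard errors. The estimate is the 3-year difference with its 95% confidence interval.
- A logistic model with only a random patient intercept is not used, for the reason shown in the table.
- The complete-pair test is reported as supportive.
- One sensitivity analysis gives missing 3-year Icon lesions the control rate. At the cited rates the Icon figure becomes 0.8 × 32 + 0.2 × 70 = 39.6%, and the difference 70 − 39.6 = 30.4 points.
- Missing at random is worded as an assumption of the main analysis.

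The cost is SAP wording and one additional analysis per outcome, using examinations and films already scheduled. The downside is a model-based estimate that is less simple than a 2×2 table.

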11.4.5 Statistical Software

The statistical software that will be used for this study is Statview.

12 Method of Reporting

12.1 Periodic Reports to the Sponsor/Monitoring

Periodic reports will be given to the sponsor in line with the frequently held monitoring visits.

The activities/reporting by the monitor that take place during the on-site visit include, but are not limited to the following:

- Only subjects who meet the study eligibility criteria are enrolled
- Informed consent process was conducted appropriately and that informed consent will be obtained prior to proceeding with any study procedures
- Data was collected and analysed as specified in the protocol
- Adverse events were reviewed promptly and reported as required
- Privacy and confidentiality of subjects was maintained
- Documentation of dropouts
- Evaluation of primary and secondary endpoints
- During an annual visit, the Monitor focuses on the areas where the majority of the deficiencies were identified or addresses other problems or issues noted since the last visit.
- The Monitor identifies and reports any suspected fraud and scientific misconduct if discovered during the review.

The clinical monitoring process of the sponsor can be classified into the following periodical visits:

Study initiation visit

The monitor conducts the study initiation visit after the sponsor submits the protocol to its IRB and in advance of study activation.

The study initiation visit is held at the study site. The monitor prepares a clinical study initiation visit report to document the study initiation visit. The PIs, Sub-Investigators, and Site Coordinators must be prepared to discuss the procedural as well as the scientific aspects of the protocol during the initiation visit.

Annual Monitoring Visit

The monitor schedules and conducts on-site monitoring visits. The first annual monitoring visit to the study site occurs 12 months after a study opens; then annually thereafter until study closure.

The monitor may conduct interim visits as requested. An interim visit can be conducted as a follow-up to an annual visit where a number of deficiencies were identified, or it can be requested for reasons such as the complexity of the study, staff changes, or number of subjects enrolled.

The annual visit is generally scheduled for two days. The monitor prepares a follow-up-monitoring report to document the visit.

Close-Out Visit

The monitor schedules the close-out visit. The close-out visit usually takes one full day. If accrual is exceptionally large, an additional day can be required.

The activities/assessments by the monitor during the close-out visit include, but are not limited to, the following:

- Complete any outstanding site monitoring tasks (e.g., regulatory review and/or review of participant records) through the date of study termination or completion;
- Confirm that the IRB has been informed of the study closure
- Ensure the PI understands follow-up requirements for reporting AEs for subjects who have completed the study
- Conduct a summary meeting with Study Principals to discuss findings and plans for resolution of outstanding issues

A final report will be prepared after finishing all monitoring activities.

13 Changes of the Clinical Investigation Plan

13.1 Amendments to the CIP

All amendments to the CIP shall be agreed to by the principal clinical investigator and be recorded with a justification for the amendments. Deviations will be reviewed to determine the need to amend the CIP or to terminate the investigation.

14 Deviations from the Clinical Investigation Plan (CIP)

14.1 Deviations from the CIP

Any deviation from the CIP will be documented together with an explanation for the deviation. Deviations will be reported to principal investigator who is responsible for analyzing the deviations and assessing their significance.

Other Reportable Information and Occurrences (ORIOs: such as protocol deviations, accidents/incidents, and compliants) will be reported to IRB in the form of an ORIO report:

- Within 7 days when urgent subjects safety or regulatory concerns exist and/or oversight letter is received
- Within 15 days when situations or event potentially alters risk-benefit assessment and/or may jeopardize integrity of study results and/or potential benefits to subjects
- With scheduled continuation review or concurrently with report to oversight body, whichever comes first, when ORIO falls outside of other IRB timeframe parameters

14.2 Withdrawal / Dropout of Subjects

Table 14.2 Withdrawal and drop-out of subjects separated by level, reason consequences

Level	Cause	Consequence
Lesion	An allocated lesion progresses radiographically into the middle or inner 1/3 of dentin (scores 4 and 5).	The lesion is treated invasively by removing the caries and placing a filling. The case is scored as "progressed" and "failure".
	The patient shows signs of reversible or irreversible pulpitis in an allocated tooth.	The tooth is treated. The case is scored as "progressed" and "failure".
Patient	The patient shows adverse reactions for one of the study materials.	Counteractive measures are taken. Unwanted effects are documented in CRF and CEF. The patient is scored as "drop out".
	The patient cannot be examined (i.e. x-ray during pregnancy)	The patient is scored as "drop out".
	One or more allocated lesions have been treated by an external dentist.	The patient is scored as "drop out".
	The patient cannot be contacted to make appointments.	The patient is scored as "drop out".
	The patient decides to withdraw his informed consent or study participation.	The patient is scored as "drop out".
Study	One or more patient(s) show severe unwanted side effects to treatment.	Individual counteractive measures are taken. The study is halted.
	More than four patients show unwanted side effects to one treatment or material used.	Individual counteractive measures are taken. The study is halted.

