18.2 Serious Adverse Events

Emergency contact details for reporting of serious adverse events are included in the CIP (Appendix A5).

Serious Adverse Events are adverse events that:

- a) led to a death,
- b) led to a serious deterioration in health that either:
 - 1) resulted in a life-threatening illness or injury, or
 - 2) resulted in a permanent impairment of a body structure or a body function, or
 - 3) required in-patient hospitalization or prolongation of existing hospitalization, or
 - 4) resulted in medical or surgical intervention to prevent life threatening illness or injury or permanent impairment to a body structure or a body function.
- c) led to fetal distress, fetal death or a congenital abnormality or birth defect.

In case of a serious adverse event and subsequent need for un-blinding the name-code list can be assessed immediately and breaking the code will not cause any further problem. The data recorded until the report of adverse event will remain included in the dataset.

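### Table 14.2 scores patients with a material reaction or no x-ray as drop-outs, although the SAP's filling outcome could still be recorded and no analysis set or missing-data analysis is defined

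*Combined protocol and SAP*

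**What the plan says.** Table 14.2 (protocol Section 14.2) sorts withdrawals into three levels.

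- **Lesion level.** Radiographic progression into deeper dentin, and pulpitis in a study tooth, count as failure.
- **Patient level.** Three rows matter here: "The patient shows adverse reactions for one of the study materials", "The patient cannot be examined (i.e. x-ray during pregnancy" and "One or more allocated lesions have been treated by an external dentist". Each leads to the patient being scored as a drop-out.
- **Study level.** The study is halted after a single severe case, or when "More than four patients show unwanted side effects to one treatment or material used".

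The SAP (Statistical Analysis) states: "The primary outcome is proportion of lesions that required restorative treatment (filling) after 3 years as measured via dental examination". The protocol is wider. Section 6.2 lists both the rate of fillings (Aim I) and radiographic change in lesion size (Aim II) as primary, and Section 11.4.3 takes progression status read from radiographs at 3 years as the outcome variable.

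On missing data, Section 11.4.4 says that the sample size allows for dropouts and adds: "The missing data will be at random". Section 18.2, on serious adverse events and unblinding, says: "The data recorded until the report of adverse event will remain included in the dataset". Neither document defines an analysis set, says whether drop-outs are still followed, or plans imputation or a sensitivity analysis.

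**The concern.** The plan does not distinguish a patient who stops a study procedure from a patient whose outcome is unknown. A reaction to a study material arises after randomisation and may be caused by the treatment. If it ends follow-up, the pairs analysed are selected partly by what the treatment did. A missed x-ray is a different matter: it has no evident link to treatment, but the patient is given up for a reason that may pass before the next visit.

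In both cases a filling can still be seen in the mouth. Discarding that information loses data and, for reactors, could bias the comparison. A bare statement that the losses are random does not address this, and the SAP gives no analysis that would show whether it matters.

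**Working it through.** **Can the outcome still be recorded?** Table 8.2 lists dental examination and radiographic examination as separate rows. It schedules a dental examination at month 6 with no film, and both at months 12, 24 and 36. (Section 9.4.2 and the SAP's six-month radiographic comparison read differently on month 6.) On Table 8.2, then, the plan already examines patients without a film, and the SAP outcome names dental examination only. The radiographic endpoint cannot be read at a visit without a film. Because radiographic progression is also a trigger for a filling in Table 14.2, filling ascertainment is weaker without films, though not impossible.

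**The plan's own figure.** Section 11.2 expects 20% loss from 150 patients: 150 × (1 − 0.20) = 120, as stated, so 30 losses are allowed for.

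**How many reactors?** The halt rule allows at most four patients per treatment or material while the study continues: 4/150 = 2.7%. I assume that adverse reactions in the drop-out row and side effects in the halt rule are the same events. The ceiling is per material, so the total over several materials could be higher.

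**Effect on the treatment difference.** Let D be the control-minus-Icon difference in n analysed pairs, and δ the mean within-pair difference in k restored pairs. The restored estimate is (nD + kδ)/(n + k), which shifts D by k(δ − D)/(n + k). For illustration D = 0.70 − 0.32 = 0.38, the 3-year split-mouth rates in Section 4.3.4. Those are progression rates, not filling rates. With n = 120, nD = 45.6.

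| Restored pairs | δ | Calculation | Difference |
|---|---|---|---|
| 4, every Icon lesion filled, no control filled | −1 | (45.6 − 4)/124 | 33.5 points |
| 4, no within-pair difference | 0 | 45.6/124 | 36.8 points |
| 4, same effect as the rest | 0.38 | (45.6 + 1.52)/124 | 38.0 points |
| 4, every control filled, no Icon lesion filled | +1 | (45.6 + 4)/124 | 40.0 points |

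The extremes are shifts of −4.5 and +2.0 points. With an assumed smaller difference of 10 points (15% against 5%), nD = 12 and the range is (12 − 4)/124 = 6.5 to (12 + 4)/124 = 12.9 points.

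**Losses without a ceiling.** The documents set no limit on x-ray losses. The outer bound, with all 30 allowed losses for every reason, is (45.6 − 30)/150 = 10.4 to (45.6 + 30)/150 = 50.4 points. This shows only what the plan leaves unexamined; nothing suggests that x-ray losses would behave that way.

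**The case against.** The strongest reply is that the harm is small and its direction unknown. In a split-mouth trial a drop-out removes both lesions, so the groups stay equal in number, and bias needs a different within-pair effect in reactors. The documents give no link between reactions and caries progression: Section 5.2 anticipates acrylate allergy with quick recovery. Pulpitis and deeper progression are already scored as failure. All of this stands, and it limits the size of the point.

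Several stronger readings are tempting, and the documents do not support them:

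- **That both rows are treatment-related exclusions.** The only x-ray example is pregnancy.
- **That excluded reactors necessarily flatter Icon.** The shift can go either way. Adding failures to the Icon arm alone overstates it, because each restored pair also brings back a control lesion.
- **That Section 18.2 discards data after a serious event.** It keeps earlier data and is silent on later data.
- **That the plan states these pairs are excluded from analysis.** This is inferred from the drop-out score and Section 11.4.4; no rule says so.
- **That missing at random is false.** A documented treatment-related reason does not by itself make it false. The fault is that it is asserted, without justification or sensitivity analysis.
- **That exposure ends on day 0.** Section 9.5 provides for repair or replacement of an unsatisfactory resin.

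A final objection is that, without films, an unfilled lesion may simply be one whose progression went unseen. That is a reason to flag such outcomes in the analysis, not to drop the patient.

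**Conclusion.** The point holds in a limited form. Table 14.2 turns two situations in which the SAP primary outcome is still recordable into drop-outs, and neither document says what then happens to those pairs. For reactions to one material, the halt rule confines the effect to between −4.5 and +2.0 points on an illustrative 38-point difference, and to zero if reactors respond like everyone else. It would matter more if the true difference in fillings were nearer 10 points. X-ray losses are an avoidable loss of data with no stated limit and no shown direction of bias.

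The conclusion rests on three assumptions: that drop-out means removal from follow-up and analysis, that the SAP's filling outcome governs the primary comparison, and that the 70% and 32% progression rates serve only as illustration.

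The external-dentist row belongs to the same problem. Treatment of a study lesion elsewhere may be the primary event itself, yet it is scored as a drop-out, with no ceiling. The change should be made: the possible bias is modest, but so is the cost.

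**What to change.** Make these changes in Table 14.2, Section 11.4.4 and the SAP together:

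1. Separate stopping study procedures from ending outcome follow-up. Outcome collection ends only when consent is withdrawn or contact is lost.
2. Define the analysis set for the filling outcome as all randomised pairs, using the 36-month dental examination that is already scheduled.
3. Treat a missed radiograph as missing for that visit's radiographic endpoint only. Flag filling outcomes ascertained without a film and examine them in a sensitivity analysis.
4. Replace the sentence asserting randomness with a stated missing-data assumption. Add a sensitivity analysis that counts the Icon lesion as failed in pairs lost after an adverse reaction, and state how the control lesion is handled.
5. State what happens to data recorded after a serious adverse event, which Section 18.2 leaves open.
6. Reconcile the external-dentist row with the SAP outcome.

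The cost is changed wording, minor analysis work and a few retained recall visits. The Icon result may look slightly less favourable.
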